4.2. Scientific Rationale for Study Design

The objective of the study is to evaluate the effect of a low-fat or high-fat meal on the relative bioavailability of PF-07284890 following single 200-mg dose oral administration using a 100 mg tablet formulation of PF-07284890 in healthy adult participants. A crossover design is used to control variability between participants and account for any period effects. Between each administered single dose, a 5-day washout is proposed to minimize any residual PF-07284890 concentrations prior to start of the next period, which is sufficient based on the observed half-life of approximately 5.7 to 10 hours ([Table 4](#)).

4.2.1. Assessment of Safety Data Before Administration of the High-fat Meal

The high-fat meal is expected to potentially increase exposures by up to approximately 2-fold.¹² Before the Period 3 doses are administered to participants that have eaten a high-fat meal, the safety data for Periods 1 and 2, including at least 8 participants (given that participants may not all be dosed at the same time) administered a low-fat meal in Period 1 or 2 and at least data from Day 1 through Day 3 of Period 2, will be reviewed by the study team and the investigator and assessed based on safety and tolerability. Period 3 will take place after a discussion between the study team and the investigator. Period 3 will initiate as planned if the doses administered in Periods 1 and 2 were well-tolerated.

Severe nonserious AEs considered as related to study intervention in 2 participants in a period would require a dose reduction. Any SAE considered related to study intervention would require a dose reduction. Dosing will be paused for any SAE that occurs in a participant receiving active treatment until causality is fully assessed by the PI and sponsor. Dosing may resume if the SAE is determined to be not drug related by the PI and sponsor. If the SAE is determined to be either drug related or unknown and is \geq severe or CTCAE Grade 3, dosing of participants will be stopped. If the SAE is determined to be either drug related or unknown and is <severe or CTCAE Grade 3, the SAE will be evaluated by the sponsor's protocol review committee (or similar review group), which is independent of the study team and investigators. If the protocol review committee determines that dosing may resume, a plan that mitigates risks to participants with the resumption of dosing will be

implemented. Such a plan could include reducing the dose or adding appropriate safety monitoring.

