6.6. Dose Modification

No dose modification is anticipated. A 200-mg dose is the maximum dose that will be administered. In case a dose reduction is necessary, the study intervention dose will be reduced or the study will be stopped early.

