- The investigator will then record all relevant AE or SAE information in the CRF.

- It is **not** acceptable for the investigator to send photocopies of the participant's medical records to Pfizer Safety in lieu of completion of the CT SAE Report Form/AE or SAE CRF page.
- There may be instances when copies of medical records for certain cases are requested by Pfizer Safety. In this case, all participant identifiers, with the exception of the participant number, will be redacted on the copies of the medical records before submission to Pfizer Safety.
- The investigator will attempt to establish a diagnosis of the event based on signs, symptoms, and/or other clinical information. Whenever possible, the diagnosis (not the individual signs/symptoms) will be documented as the AE or SAE.

Assessment of Intensity

The investigator will make an assessment of intensity for each AE and SAE reported during the study and assign it to 1 of the following categories:

- Mild: A type of AE that is usually transient and may require only minimal treatment or therapeutic intervention. The event does not generally interfere with usual ADL.
- Moderate: A type of AE that is usually alleviated with additional specific therapeutic intervention. The event interferes with usual ADL, causing discomfort, but poses no significant or permanent risk of harm to the research participant.
- Severe: A type of AE that interrupts usual ADL, or significantly affects clinical status, or may require intensive therapeutic intervention.

An event is defined as "serious" when it meets at least 1 of the predefined outcomes as described in the definition of an SAE, NOT when it is rated as severe.

Assessment of Causality

- The investigator is obligated to assess the relationship between study intervention and each occurrence of each AE or SAE. The investigator will use clinical judgment to determine the relationship.
- A "reasonable possibility" of a relationship conveys that there are facts, evidence, and/or arguments to suggest a causal relationship, rather than a relationship cannot be ruled out.

- Alternative causes, such as underlying disease(s), concomitant therapy, and other risk factors, as well as the temporal relationship of the event to study intervention administration, will be considered and investigated.
- The investigator will also consult the IB and/or product information, for marketed products, in their assessment.

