- For each AE or SAE, the investigator **must** document in the medical notes that they have reviewed the AE or SAE and have provided an assessment of causality.
- There may be situations in which an SAE has occurred and the investigator has minimal information to include in the initial report to the sponsor. However, **it is very important that the investigator always make an assessment of causality for every event before the initial transmission of the SAE data to the sponsor.**
- The investigator may change their opinion of causality in light of follow-up information and send an SAE follow-up report with the updated causality assessment.
- The causality assessment is one of the criteria used when determining regulatory reporting requirements.
- If the investigator does not know whether or not the study intervention caused the event, then the event will be handled as “related to study intervention” for reporting purposes, as defined by the sponsor. In addition, if the investigator determines that an SAE is associated with study procedures, the investigator must record this causal relationship in the source documents and CRF, and report such an assessment in the dedicated section of the CT SAE Report Form and in accordance with the SAE reporting requirements.

Follow-Up of AEs and SAEs

- The investigator is obligated to perform or arrange for the conduct of supplemental measurements and/or evaluations, as medically indicated or as requested by the sponsor, to elucidate the nature and/or causality of the AE or SAE as fully as possible. This may include additional laboratory tests or investigations, histopathological examinations, or consultation with other healthcare providers.
- If a participant dies during participation in the study or during a recognized follow-up period, the investigator will provide Pfizer Safety with a copy of any postmortem findings, including histopathology.

- New or updated information will be recorded in the originally submitted documents.
- The investigator will submit any updated SAE data to the sponsor within 24 hours of receipt of the information.

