6. ANALYSES AND SUMMARIES

6.1. Primary Endpoints

The primary endpoints are the ratios of AUC_{last} , AUC_{inf} (if data permit) and C_{max} of PF-07284890 under the fed conditions (low-fat meal or high-fat meal), relative to the PK parameters under the fasted condition.

Using data from Treatments A and B, natural log transformed AUC_{inf} (if data permit), AUC_{last} and C_{max} will be analyzed using a mixed effect model with sequence, period and treatment as fixed effects and participant within sequence as a random effect. Estimates of the adjusted mean differences (Test-Reference) and corresponding 90% CIs will be obtained from the model. The adjusted mean differences and 90% CIs for the differences will be exponentiated to provide estimates of the ratio of adjusted geometric means (Test/Reference) and 90% CI for the ratios. Treatment A (PF-07284890 under fasted condition) is the Reference treatment and Treatment B (PF-07284890 administered under fed condition, low-fat meal) is the Test treatment.

Using data from Treatments A and C, natural log transformed AUC_{inf} (if data permit), AUC_{last} and C_{max} will be analyzed using a mixed effect model with treatment and sequence as a fixed effect and participant within sequence as a random effect. Estimates of the adjusted mean differences (Test-Reference) and corresponding 90% CIs will be obtained from the model. The adjusted mean differences and 90% CIs for the differences will be exponentiated to provide estimates of the ratio of adjusted geometric means (Test/Reference) and 90% CI for the ratios. Treatment A (PF-07284890 under fasted condition) is the Reference treatment and Treatment C (PF-07284890 administered under fed condition, high-fat meal) is the Test treatment.

Residuals from the model will be examined for normality and the presence of outliers via visual inspection of plots of residuals vs predicted values and normal probability plots of residuals but these will not be included in the CSR. If there are major deviations from normality or outliers then the effect of these on the conclusions will be investigated through alternative transformations and/or analyses excluding outliers. Justification for any alternative to the planned analysis will be given in the report of the study.

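### Protocol Section 4.2.1 makes a dose reduction both mandatory and optional after a related SAE below severe or CTCAE Grade 3

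*Protocol*

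**What the plan says.** The second paragraph of Protocol Section 4.2.1 sets out what follows an SAE. Near its start is a rule without qualification: "Any SAE considered related to study intervention would require a dose reduction". The paragraph then pauses dosing for any SAE while causality is assessed, and allows dosing to resume if the event is judged unrelated. For an SAE judged related, or of unknown cause, it next divides by severity.

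- At or above the threshold, the rule ends "or CTCAE Grade 3, dosing of participants will be stopped".
- Below the threshold, the sponsor's protocol review committee, which is separate from the study team and the investigators, evaluates the event. The text continues "If the protocol review committee determines that dosing may resume, a plan that mitigates risks to participants", and describes the content of that plan as follows: "Such a plan could include reducing the dose or adding appropriate safety monitoring".

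Protocol Section 6.6 does not anticipate any dose modification, but adds: "In case a dose reduction is necessary, the study intervention dose will be reduced or the study will be stopped early".

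**The concern.** The opening rule and the committee rule both cover a related SAE below severe or CTCAE Grade 3, and they do not prescribe the same thing. One reader will take a reduction as fixed and see the committee as deciding only whether dosing resumes. Another will take the committee as free to approve resumption at the unchanged dose with extra monitoring. The second reader's plan would breach the opening rule.

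The paragraph would be used under time pressure, with dosing paused, in healthy participants who gain no clinical benefit. It also comes ahead of a high-fat dose that the same section expects may raise exposure by up to about 2-fold. Protocol Section 10.1.4 provides no external data monitoring committee, so the protocol review committee is the independent body that Section 4.2.1 names for this decision. Its remit should not depend on which sentence a reader gives priority.

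**Working it through.** No arithmetic applies, and the plan gives no figure to reproduce. The check sets the rules side by side for an SAE judged related to study intervention.

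| Severity of the related SAE | Opening rule in 4.2.1 | Later rule in 4.2.1 | Section 6.6 | Result |
|---|---|---|---|---|
| Below severe or Grade 3 | Reduction required | Committee may allow resumption; reduction is one option, added monitoring another | Reduce or stop early | Contradiction if the plan is monitoring alone |
| Severe or Grade 3 and above | Reduction required | Dosing stopped | Reduce or stop early | Mismatch in wording, largely bridged by 6.6 |

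**Step 1: is the lower row empty?** It would be if every SAE were severe by definition. Appendix 3 (Section 10.3.3) rules this out. Seriousness depends on meeting an outcome criterion "described in the definition of an SAE, NOT when it is rated as severe". A related SAE can therefore be mild or moderate, and Section 4.2.1 itself provides a separate branch for events below the threshold.

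**Step 2: can both rules be followed in the lower row?** They can if the committee happens to choose a reduction. They cannot if it chooses monitoring alone, which the later sentence offers as an alternative. If the opening rule always applies, that alternative has no effect for related events. If the later rule governs, the opening rule does not hold for every related SAE.

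**Step 3: is there an order of precedence?** No wording of exception or priority links the two rules within Section 4.2.1. Section 6.6 starts from the premise that a reduction is necessary, which is the point in dispute here, and it has no monitoring-only route. Sections 7.1, 7.2 and 8.1 concern whether a participant continues or is discontinued. Appendix 3 concerns recording, grading, causality and reporting. The SAP has no rule on the matter.

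**Step 4: the upper row.** The opening rule asks for a reduction and the later rule stops dosing. Section 6.6 names early stopping as an alternative when a reduction is called for, and the severity threshold in Section 4.2.1 can be read as the criterion for choosing it. What is left is that the opening sentence, taken alone, does not describe this branch.

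**The case against.** The strongest reply is that the committee sentences cover two causality classes, related and unknown, and that the list of plan contents is permissive. A reduction could then be the minimum for related events, with monitoring alone kept for events of unknown cause. That reading is coherent and would remove the contradiction, but the paragraph does not state it. The plan sentence offers both options without separating the two classes. It could equally be said that the specific later rule overrides the general one, or that the opening rule concerns only the decision to start Period 3. Neither is written down, and a related SAE in Period 1 or 2 would come under both rules anyway. That several harmonising readings are available, leading to different actions, supports asking for a clarification.

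A second reply stands in full: the safeguards limit the consequence. Any SAE pauses dosing first, and in the disputed branch dosing resumes only after independent review and with a mitigation plan. On no reading does dosing continue by default.

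Three stronger inferences are tempting but not supported.

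- A reader might see the stop rule as an equally serious contradiction. Section 6.6, read with the severity threshold, largely reconciles it.
- A reader might extend the conflict to SAEs of unknown cause, because Appendix 3 says "If the investigator does not know whether or not the study intervention caused the event, then the event will be handled as" related. That sentence is limited to reporting, and Section 4.2.1 itself keeps related and unknown apart, so only the later rules apply to unknown causality.
- A reader might infer that a reduced dose would bias the food-effect ratios. The SAP's fasted versus high-fat model begins "Using data from Treatments A and C, natural log transformed", and both documents define Treatments A, B and C as 200 mg. Bias would need a reduced-dose period to be coded as one of those treatments, and nothing in the documents provides for that.

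**Conclusion.** Wrong as written, in one place. For a related SAE below severe or CTCAE Grade 3, Section 4.2.1 contains two rules that differ on whether a dose reduction is required, and neither document says which prevails. This is one of the two severity levels for a related SAE. The other has a secondary wording mismatch that Section 6.6 largely resolves. The rules for unrelated SAEs and for SAEs of unknown cause are not affected.

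The conclusion rests on the text alone and needs no assumption about how often such an event would occur. The documents give no rate of related SAEs, so no probability is attached. The defect concerns an operating rule for safety, and has no bearing on the sample size, the primary models or the confidence intervals.

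**What to change.** Reconcile Sections 4.2.1 and 6.6 so that each severity level of a related SAE leads to one stated consequence. In particular:

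- State whether the protocol review committee may approve resumption without a dose reduction for a related SAE below severe or Grade 3, and word the opening rule to match.
- Make the opening rule consistent with the branch at or above the threshold, and tie the choice in Section 6.6 between reducing and stopping to the same severity levels.

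Which consequence applies at each level is a clinical decision for the sponsor, and this review takes no position on it. The cost is wording in two protocol sections. The schedule, sample size and SAP models stay as they are.

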4.2.2. Choice of Contraception/Barrier Requirements

Nonclinical studies suggest risk for severe manifestations of developmental toxicity at relevant clinical exposures for PF-07284890. Therefore, the use of a highly effective method of contraception is required (see [Appendix 4](#)).

4.2.3. Collection of Retained Research Samples

Retained Research Samples will be collected and stored for further analyses which may, for example, provide greater understanding of the study intervention.

CCI
[REDACTED]
[REDACTED]
[REDACTED]

4.3. Justification for Dose

A single 200 mg dose of PF-07284890 is planned for each period of this study.

Following 28 days of once-daily oral administration of PF-07284890 (10, 30 or 60 mg/kg) to Sprague Dawley rats (the sensitive species) in a GLP toxicology study, the STD₁₀ was 60 mg/kg. For the lowest dose of 10 mg/kg, exposures in male and female rats, respectively, are estimated to be 12-32 multiple over those of the planned clinical dose (ie, see details in [Section 2.2.3](#)). The effect of food on PF-07284890 exposures based on its properties (Biopharmaceutics Classification System Class II compound, weak base) is expected to be less than a 2-fold increase;¹² a 2-fold increase in human exposures would reduce these margins to be ~6-16 multiple over those of the planned clinical dose. The clinical data from C4471001 are also important for justifying the 200 mg dose.

Clinical experience with PF-07284890 is based on the FIH study, C4471001, in which dose-finding is being conducted based on the safety and PK of repeat doses of PF-07284890. As of 10 January 2022, the study has dosed 22 patients in the Phase 1a Dose Escalation. At the 4 monotherapy dose levels assessed (50 mg QD, 100 mg QD, 200 mg QD, and 200 mg BID), 12 patients have been treated, 9 patients were DLT evaluable, and no patients experienced DLTs ([Table 2](#)).

Preliminary safety results of the 200 mg QD dose of PF-07284890 in patients resulted in treatment emergent adverse events of Grade 2 worsening gout related to underlying condition and sinus infection/sinusitis as well as Grade 1 anorexia, arthritis, back pain, nausea and pain, all in 1 patient each. With repeat dosing of the 200 mg BID dose schedule, one patient experienced Grade 3 pneumonia, considered not related to study drug. Grade 2 events, occurring in 1 patient each, were ejection fracture decreased considered related to the patient's underlying disease, fatigue, and oxygen saturation decreased preceding diagnosis of

pneumonia, as well as maculo-papular rash. Dizziness, dry skin, and benign skin lesion were reported in 1 patient each as Grade 1. At lower doses, the only severe events reported were fatal disease progression of cancer, suprapubic pain related to the patient's underlying disease, and 2 patients with Grade 3 anemia, considered unrelated to study treatment in 1 case, and in another patient with Grade 1 anemia at baseline in the setting of renal dysfunction and iron deficiency. Data from repeat-dosing in patients suggests that the 200 mg dose is well tolerated.

Based on clinical PK data, the AUC_{24hr} from the highest tolerated dose of 200 mg BID is estimated to be approximately 3.4-fold higher than the AUC_{24hr} for a single dose of 200 mg (ie, based on the accumulation ratio of 1.69 observed for 100 mg BID administration, [Table 5](#), compared to a single dose, BID administration can be expected to have approximately 2×1.69 -fold higher AUC_{24hr}). Food may increase the AUC_{24hr} , but this 3.4-fold margin based on fasted-state PK increases confidence in the safety of the single daily dose given one time every 5 days for 3 doses. The 5-day interval between doses is expected to avoid any accumulation.

A single dose of 200 mg PF-07284890 given once every 5 days for 3 doses is considered safe to be used in healthy volunteers.

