Based on the requirement for euthanasia, due to the impairment of mobility and pain (due to paw/hind limb swelling) at the lower dose level, the NOAEL could not be determined. However, these skin effects were not seen in rats until Study Day 10 and a single female required euthanasia due to this effect. The STD₁₀ of 60 mg/kg was determined from test article-related lethality or irreversible and life-threatening findings. The lowest dose of 10 mg/kg corresponded to plasma AUC_{24hr} on Study Day 1 of 192 and 517 µg•hr/mL in male and female rats respectively, 12-32 multiple over the planned clinical dose (Table 1) based on comparison to the geometric mean AUC_{24hr} for a 200-mg single dose (ie, based on C1D1) as shown in [Table 4](#).

Table 1. MOEs for Nonclinical Species Compared to Humans at Dose Levels of Interest^a

Subject area	Key Findings	Margin for HV C1D1 (AUC)	Margin for HV C1D1 (C _{max})
General Tox Rat 28-Day Study QD oral 10, 30, 60 m/k/d (473.05)	Beginning on Study Day 10 skin effects with rash and/or paw and hindlimb swelling all doses (10 mg/kg margin shown)	Male = 12x Female = 32x	Male = 13x Female = 21x
	Myxomatous degeneration of heart valves, degeneration of seminiferous tubules of testes with decreased sperm in the epididymis at >30 mg/kg	30 mg/kg M = 39x 30 mg/kg F = 74x	30 mg/kg M = 35x 30 mg/kg F = 55x
	NOAEL not achieved due to impairment of mobility from hind limb swelling and pain requiring euthanasia at 10 mg/kg (a single female rat) (10 mg/kg MOE shown)	Male = 12x Female = 32x	Male = 13x Female = 21x

Table 1. MOEs for Nonclinical Species Compared to Humans at Dose Levels of Interest^a

Subject area	Key Findings	Margin for HV C1D1 (AUC)	Margin for HV C1D1 (C _{max})
	STD ₁₀ 60 mg/kg based on 4/32 early terminated animals	Male = 59x Female = 110x	Male = 41x Female = 67x
General Tox NHP 28-Day Study QD oral 10, 30, 100 m/k/d (473.04)	Well tolerated for 28 days		
	Minimal stomach ulceration 100 mg/kg	5x	8x
	NOAEL and HNSTD 100 mg/kg	5x	8x

a. Exposures from nonclinical TK data were divided by human monotherapy geometric mean AUC_{24hr} and C_{max} values as appropriate at the 200 mg dose level (data shown in Table 4).

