2.2.4.2. Summary of PF-07284890 Pharmacokinetics in Human

Single and repeat dose PK data from study C4471001 for monotherapy (Table 4) and for combination therapy when coadministered with binimetinib (Table 5) have been obtained under fasted conditions. PF-07284890 plasma exposure increased in a less than dose proportional manner. For monotherapy, the geometric mean dose-normalized AUC_{24hr} for the 200 mg QD dose was approximately 1.83- and 1.43-fold higher than for the 50-mg dose on C1D1 and C1D15, respectively, when a 4-fold increase would be expected for linear PK. The T_{max} ranged from 1.5 to 6.0 hours across dose groups. The median $t_{1/2}$ across dose groups ranged from 5.7 to 10 hours. PF-07284890 exposures were somewhat higher for combination therapy than for monotherapy, with the difference attributable to PK variability.

The accumulation ratio based on AUC values, R_{AUC} , for patients administered PF-07284890 QD ranged from 0.709 to 1.31, suggesting limited accumulation for QD administration. For BID administration, the limited available data indicate more accumulation occurs, with an R_{AUC} value of 1.69 for the 100 mg BID combination therapy cohort.

Table 4. PF-07284890 Plasma PK Parameters Observed During Monotherapy Dose Escalation in C4471001^a

PF-07284890 Dose and Regimen	Cycle and Day (N)	C_{max} , ng/mL	T_{max} , hr	AUC_{τ} , ng hr/mL	C_{trough} , ng/mL ^b	$t_{1/2}$, hr	R_{Cmax}	R_{AUC}
50 mg QD	C1D1 (2)	795	1.5	8850	—	6.17 ^c	—	—
	C1D15 (2)	1440	1.5	11500	166	10.0	1.79	1.31
100 mg QD	C1D1 (4)	1610 (40.3)	5.0	14400 (40.5)	—	5.83	—	—
	C1D15 (3)	1090 (16.2)	4.0	10400 (8.34)	115 (71.7)	9.11	0.703 (37.1)	0.709 (45.2)

Table 4. PF-07284890 Plasma PK Parameters Observed During Monotherapy Dose Escalation in C4471001^a

PF-07284890 Dose and Regimen	Cycle and Day (N)	C _{max} , ng/mL	T _{max} , hr	AUC _τ , ng hr/mL	C _{trough} , ng/mL ^b	t _½ , hr	R _{Cmax}	R _{AUC}
200 mg QD	C1D1 (3)	1580 (20.3)	6.0	16200 (22.5)	—	5.68	—	—
	C1D15 (3)	1820 (15.5)	2.0	16500 (8.12)	116 (329)	9.64	1.15 (36.6)	1.02 (14.3)
200 mg BID	C1D1 (3)	1890 (39.2)	6.0	17000 ^d	—	—	—	—
	C1D15	ND	ND	ND	ND	ND	ND	ND

- a. Analysis includes bioanalytical data available through 21DEC2021, and results are preliminary data that did not use the actual sample times. Values are Geometric mean (geometric %CV) except for when N <3, for which median values are presented, and for T_{max} and t_½, where median is presented. ND = no data.

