10.10. Appendix 10: Abbreviations

The following is a list of abbreviations that may be used in the protocol.

Abbreviation	Term
%CV	percent coefficient of variation
Abs	absolute
ADL	activity/activities of daily living
AE	adverse event
AESI	adverse event of special interest
AKI	acute kidney injury
ALP	alkaline phosphatase
ALT	alanine aminotransferase
ANC	absolute neutrophil count
aPTT	activated partial thromboplastin time
AST	aspartate aminotransferase
ATC	anaplastic thyroid cancer
AUC	area under the plasma concentration-time curve
AUC _{24hr}	area under the plasma concentration-time curve from time zero to 24 hours
AUC _{inf}	area under the plasma concentration-time curve from time zero extrapolated to infinity
AUC _{last}	area under the plasma concentration-time profile from time zero to the time of the last quantifiable concentration (Clast).
AUC _{tau}	area under the plasma concentration-time curve from time zero to tau (ie, over the dosing interval)
AV	atrioventricular
AxMP	auxiliary medicinal product
BBS	Biospecimen Banking System
BCRP	breast cancer resistance protein
BID	twice daily
BLRM	Bayesian Logistic Regression Model
BMI	body mass index
BP	blood pressure
bpm	beats per minute
BRAF	B-type Raf proto-oncogene
BRAFi	B-type Raf proto-oncogene inhibitor
BUN	blood urea nitrogen
C1D1	Cycle 1 Day 1
C1D15	Cycle 1 Day 15
CFR	Code of Federal Regulations
CI	confidence interval
CIOMS	Council for International Organizations of Medical Sciences
CK	creatine kinase
CKD-EPI	chronic kidney disease epidemiology

PFIZER CONFIDENTIAL

Abbreviation	Term
CL/F	apparent clearance
C_{last}	the last quantifiable concentration
C_{max}	maximum observed concentration
CNS	central nervous system
CO ₂	carbon dioxide (bicarbonate)
COVID-19	coronavirus disease 2019
Cp	plasma concentration
CR	complete response
CRC	colorectal cancer
CRF	case report form
CRO	contract research organization
CRU	clinical research unit
CSR	Clinical Study Report
CT	clinical trial
CTCAE	Common Terminology Criteria for Adverse Events
CTIS	Clinical Trial Information System
CTMS	Clinical Trial Management System
C_{trough}	pre-dose plasma concentration
CYP	cytochrome P450
DCT	data collection tool
DDI	drug-drug interaction
DICI	drug-induced creatinine increase
DIKI	drug-induced kidney injury
DILI	drug-induced liver injury
DLT	dose-limiting toxicity
DME	drug metabolizing enzyme
DNA	deoxyribonucleic acid
DoR	duration of response
EC	ethics committee
ECC	emergency contact card

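### The 3.4-fold exposure margin in Protocol Section 4.3 sets a 24-hour steady-state exposure against a 12-hour first-dose exposure; a like-for-like 24-hour margin is about 2.4 (roughly 2.0 to 2.7)

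*Protocol*

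**What the plan says.** Section 4.3 of the protocol justifies a single 200 mg dose per period in healthy volunteers. One of its supports is clinical exposure: AUC24hr on 200 mg BID is put at about 3.4 times the AUC24hr of one 200 mg dose, calculated as 2 × 1.69. The section acknowledges that food may raise exposure, and answers that "this 3.4-fold margin based on fasted-state PK increases confidence in the safety of the single daily dose given one time every 5 days".

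The 1.69 comes from Section 2.2.4.2 and Table 5, which give an R_AUC "value of 1.69 for the 100 mg BID combination therapy cohort". A table footnote says it could be determined for only 3 subjects. The AUC column in Tables 4 and 5 is AUCtau, defined in Appendix 10 as "area under the plasma concentration-time curve from time zero to tau (ie, over the dosing interval".

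Elsewhere the protocol uses AUC24hr in its literal sense. Section 2.2.3 compares the rat exposures with the "geometric mean AUC_{24hr} for a 200-mg single dose (ie, based on C1D1) as shown in" Table 4, which is the once-daily C1D1 value of 16200 ng·hr/mL. Section 4.3 then halves the rat margins, from 12-32 to about 6-16, for a 2-fold food effect. It does not do this for the 3.4.

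**The concern.** A BID accumulation ratio compares one 12-hour interval at steady state with the first 12-hour interval. Multiplying by 2 extends the numerator to 24 hours and leaves the denominator at 12. Whatever exposure a single dose adds between 12 and 24 hours is left out, so the ratio is larger than a true AUC24hr ratio.

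The 3.4 is the only margin in Section 4.3 based on human exposure, and the text sets it directly against the food effect. Section 4.2.1 allows for an increase of up to about 2-fold with the high-fat meal. A reader weighing risk in a study with no benefit to participants would take from 3.4 that a comfortable margin remains after food. The corrected figure leaves much less.

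**Working it through.** **Inputs.** R_AUC 1.69 (100 mg BID combination, Table 5). Single-dose 200 mg AUC24hr 16200 ng·hr/mL (200 mg QD, C1D1, Table 4). R_AUC 1.02 (200 mg QD, Table 4). Median half-life, which Section 2.2.4.2 says "across dose groups ranged from 5.7 to 10 hours". Tmax, which "ranged from 1.5 to 6.0 hours across dose groups". The 12-hour interval for BID is inferred from the definition of AUCtau; the tables do not print it.

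**1. The plan's figure.** 2 × 1.69 = 3.38, which rounds to 3.4.

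**2. What that is a ratio of.** R_AUC(BID) = AUC(0-12, steady state) / AUC(0-12, first dose). Doubling gives AUC(0-24, steady state) / AUC(0-12, first dose).

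**3. What the protocol means by single-dose AUC24hr.** The rat AUCs of 192 and 517 µg·hr/mL give 192/16.2 = 12 and 517/16.2 = 32, matching Table 1. There the denominator is a full 24 hours.

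**4. Like-for-like formula.** Margin = 2 × R_AUC × AUC(0-12)/AUC(0-24), the last two after a first dose. For mono-exponential decline with half-life t, let x = 2^(-12/t). Then AUC(0-12)/AUC(0-24) = 1/(1 + x). Under linear superposition R_AUC = 1/(1 - x), so the margin is 2/(1 - x²) = 2/(1 - 2^(-24/t)).

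**5. Results by route.**

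- Half-life implied by 1.69: x = 1 - 1/1.69 = 0.408, t = 9.3 h, margin 3.38/1.408 = **2.40**.
- Stated half-lives throughout: 2.11 at 5.7 h and 2.47 at 10 h. Their own R_AUC values would be 1.30 and 1.77.
- Stated half-lives with one-compartment absorption, Tmax 1.5 to 6 h: 2.12-2.26 at 5.7 h and 2.48-2.63 at 10 h.
- Keeping 1.69 and using the half-life only to extend the denominator: 3.38/(1 + 0.232) = 2.74 at 5.7 h and 3.38/(1 + 0.435) = 2.36 at 10 h. Adding absorption to this route gives 2.02 to 2.70.
- The observed 24-hour accumulation ratio at this dose: 2 × 1.02 = 2.04.

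These run from about 2.0 to 2.7, with 2.4 as a central value.

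**6. Consistency check.** For 2/(1 - 2^(-24/t)) to equal 3.38, 2^(-24/t) = 1 - 2/3.38 = 0.408, so t = 18.6 h, and R_AUC would be 2.77. Section 4.2 calls the 5-day washout one "which is sufficient based on the observed half-life of approximately 5.7 to 10 hours". This check uses the same linear model as step 5, so it illustrates the mismatch and is not separate evidence for it.

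**7. After a 2-fold food effect.** 2.40/2 = 1.20; 2.04/2 = 1.02; 2.74/2 = 1.37; the stated figure, 3.38/2 = 1.69.

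**The case against.** The best case for the protocol does not dispute the time windows; nothing in the documents reconciles them. It concerns the replacement number and its weight, and much of it stands.

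- **The model is simple and the data strain it.** Section 2.2.4.2 reports that "PF-07284890 plasma exposure increased in a less than dose proportional manner". In Table 4 the half-life lengthens from C1D1 to C1D15 in every once-daily cohort (6.17 to 10.0, 5.83 to 9.11 and 5.68 to 9.64 h), whereas the formula needs it constant. No BID cohort has a reported half-life, and 200 mg BID has no C1D15 data. So 2.4 is illustrative, and a range as narrow as 2.1 to 2.5 would claim too much.
- **The sparse data cannot exclude 3.4.** With a geometric CV of 31.0% in 3 patients, and assuming log-normality, the 90% interval for 1.69 is about 1.0 to 2.8, which just includes the 2.77 of step 6. Across cohorts, 3.38 × 17000/16200 = 3.5 while 2 × 16400/18000 = 1.8. These compare different patients in groups of 2 to 4. The first also borrows the 1.69 and is not how the protocol derived its figure. A reader might infer that the true ratio has been shown to be below 3.4; the documents do not support that. They show that 2 × 1.69 does not estimate the quantity named.
- **It is one hedged, supporting sentence.** The text shows its derivation, calls the figure an estimate and notes that it rests on fasted PK. No stopping rule, endpoint, sample size or analysis uses it. This limits the consequence, but it does not make the figure right.

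**Conclusion.** The mismatch of time windows is clear from the protocol's own definitions, and confidence in that part is high. The stated 3.4 is a 24-hour exposure over a 12-hour exposure, and it errs in the reassuring direction. Against the like-for-like estimates it is too large by a factor of 3.38/2.40 = 1.41, with a range of 3.38/2.74 = 1.23 to 3.38/2.04 = 1.66.

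The replacement, about 2.4 (roughly 2.0 to 2.7), is conditional. It assumes approximately linear PK and leans on 1.69 from 3 combination-therapy patients, or on half-lives and a once-daily ratio from equally small cohorts. After a full 2-fold food effect it leaves about 1.2 (roughly 1.0 to 1.4).

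A reader might go further and conclude that 200 mg with food is not justified. The documents do not support that. Section 4.3 expects a food effect of less than 2-fold, which the corrected margin still covers, though with little room. The fed rat margins of about 6-16 do not depend on this figure. Neither do the repeat-dose tolerability in patients, the dose-reduction and stopping rules, or the Section 4.2.1 safety review, with at least 8 low-fat-meal participants, before high-fat dosing. This is a supporting safety figure that should be corrected.

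**What to change.** Revise the exposure-margin paragraph of Section 4.3:

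- Compute both sides over 0-24 h and replace 3.4-fold with about 2.4-fold (roughly 2.0 to 2.7, depending on the half-life, absorption and accumulation ratio used).
- State that this assumes approximately linear PK, that 1.69 comes from 3 patients on combination therapy, and that there are no steady-state PK data at 200 mg BID.
- Carry the up-to-2-fold food effect through, giving about 1.2 (roughly 1.0 to 1.4), as the section already does for the rat margins.

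The cost is a short text change and a less favourable stated margin. Dose, design, analysis and stopping rules stay as they are, and the SAP needs no change.
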